### **5.4 Missing, Unused & Spurious Data**

Attempts will be made to complete any missing data. In addition, the means and ranges of all variable distributions and outlying data or improbable combinations of variables will be examined before analysis is undertaken. Queries will be sent to investigators for inconsistent or missing data. Endpoint analysis will be performed with and without using imputation of missing data (where applicable) to estimate the effect of missing data on ITT and PP population. Differences between their results will be summarized and discussed.

## **6. Data Collection & Reporting**

### **6.1 Method of Data Collection & Documentation**

The Sponsor will provide the center with the Registry Plan, electronic Case Report Forms (eCRF) and all other necessary documentation to perform the registry.

### **6.2 Protocol Deviations**

Investigators may not deviate from the registry plan, unless to protect the health and safety of a participant. Any deviations from the protocol must be reported to the Sponsor as soon as possible and no later than 10 calendar days. Deviations will be assessed by the Sponsor and corrective and preventive action plans (CAPA) may be implemented to avoid future deviations. Deviations will be reported to the REB/IRB according to reporting guidelines.

### **6.3 Electronic Case Report Form (eCRF)**

Registry data will be documented on a web-based eCRF. The eCRF is provided by the Sponsor and will be used to record data that are integral to the registry and subsequent reports. The Sponsor will obtain

evidence of verification, validation and security of the eCRF platform. All collected data will be de-identified and reside in Canada.

The eCRF must be accurate and complete. All participant data entered onto the eCRF should be supported by source documents (e.g., medical records). The eCRFs are completed for each enrolled participant and signed by the Investigator.

Because of the potential for errors, inaccuracies, and illegibility in transcribing data onto eCRF, originals of all relevant procedural records and reports, post-procedural examinations, laboratory and other test results should be kept on file in each participant's medical file as permissible by each site's record keeping policy. The eCRF must be kept current to reflect participant's status during the course of the registry.

The Sponsor will train each participating center in this registry on the proper use of the eCRF.

#### **6.4 Data Management**

The Investigator shall enter all participant data into a web-based registry database. Only de-identified participant data will be collected to ensure and maintain participant privacy. The database will be maintained within Canada and will comply to all relevant privacy laws.

#### **6.5 Data Quality Control & Assurance**

Data entry will be reviewed on a regular basis. Quality control audits of all key performance and safety data in the database will be made after the sites complete enrollment and prior to database lock.

The Sponsor (or delegate) will oversee all aspects of data quality. The data will be monitored according to the Monitoring Plan through central and remote monitoring strategies. Outlier data will be queried and remote access to electronic medical records (EMR) may be requested for source data verification (SDV).

Each clinical site will be monitored according to the study monitoring plan to ensure to verify that:

- The rights and well-being of the participants are protected
- The reported study data are accurate, complete and verifiable from source documents
- The conduct of the study is in compliance with the currently approved Clinical Investigation Plan (CIP)/ amendment(s), ICH GCP, ISO 14155:2020, 21 CFR parts 50, 54 and 56, and applicable requirements of the REB/IRB
- There is adequate participant enrollment

#### **6.6 Registry Records Retention**

It is the responsibility of the investigator to maintain a comprehensive and centralized filing system of all relevant study documentation. Investigators will be instructed to retain all study records required by the Sponsor in a secure and safe facility with limited access for one of the following time periods based on sponsor notification:

- A period of at least two years after completion of the registry
- Or longer as required by local regulations

The investigator will be instructed to consult with the Sponsor before disposal of any study records and to provide written notification to the Sponsor of any change in the location, disposition, or custody of the registry documentation.

## 7. Safety

### 7.1 Definition and assessment of safety related events

Information on safety related events will be collected during the Device Period of the registry by the investigators or their designate. Classification of events is based on ISO 14155:2020.

- Adverse Event (AE): any untoward medical occurrence, unintended disease or injury, or untoward clinical signs (including abnormal laboratory findings) in participants, users or other persons, whether or not related to the device. This definition includes events related to the procedures involved.
- Serious Adverse Events (SAE): An adverse event that led to death or led to serious deterioration in the health of the participant, that either resulted in:
  - Death
  - A life-threatening illness or injury, or
  - A permanent impairment of a body structure or a body function, or
  - In-patient or prolonged hospitalization, or
  - Medical or surgical intervention to prevent life-threatening illness or injury or permanent impairment to a body structure or a body function, or
  - Fetal distress, fetal death or a congenital abnormality of birth defect.

Planned hospitalization for a pre-existing condition, or a procedure required by the clinical investigation plan without serious deterioration in health, is not considered a serious adverse event.

- Adverse Device Effect (ADE): An adverse event related to the use of the device. This definition includes adverse events resulting from insufficient or inadequate instructions for use, deployment, implantation, installation or operation, or any malfunction of the device. This definition includes any event resulting from use error or from intentional misuse of the medical device.
- Serious Adverse Device Effect (SADE): Adverse device effect that has resulted in any of the consequences characteristic of a serious adverse event.
- Device Deficiency (DD): inadequacy of a medical device with respect to its identity, quality, durability, reliability, usability, safety or performance. Device deficiencies include malfunctions, use errors, and inadequacy in the information supplied by the manufacturer including labelling.

### 7.2 Reportable Events

For the purpose of this post market registry and per the study AE CRF, the following adverse events of interest and device deficiencies will be collected:

- Adverse reaction to material

- Device Migration
- Inaccurate location detection
- Inaccurate deployment
- Infection
- Tissue/vascular trauma
- Other: any AE that, in the opinion of the investigator, has a causal relationship (probable or definite) to the device or procedure, or any device deficiency, whether or not associated with an adverse event.

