### 7.3 Reporting of safety related events

Adverse events and DD will be collected from the time the reflector is inserted into the participant (at biopsy) to the time the reflector is removed at surgery (Device Period) or until a study completion form is completed. Any AE in this period, either serious, non-serious, whether deemed device-related or not, must be reported to the Sponsor immediately after the investigator or coordinator has become aware of its occurrence. Reporting of an AE or DD to the Sponsor should take place within 24 hours upon becoming aware of the event, but not later than 3 calendar days. All AE (serious or non-serious) and DD will be documented in the eCRF. The AE/DD eCRF page should be submitted to the Sponsor within 24 hours even if all of the information is not available at the time of the initial contact. Sponsor contact for reporting: .

The investigator will evaluate (S)AEs with regard to causality and seriousness.

Reporting of serious incidents to the regulatory authorities will be reported per local regulations:

- Incident means any malfunction or deterioration in the characteristics and/or performance of the SCOUT® Surgical Guidance system, including use-error due to ergonomic features, any inadequacy in the information supplied by the manufacturer and any undesirable side-effect.
- Serious incident means any incident that directly or indirectly led, might have led or might lead to any of the following:
  - Death of a participant, user or other person,
  - Temporary or permanent serious deterioration of the participant's, user's or other person's state of health,
  - Serious public health threat;

Safety related events, which require preventive or corrective measurements intended to protect participants, may have to be reported to the local REBs/IRBs. The Sponsor will notify all other involved sites to report to their respective REBs/IRBs according to their requirements. The Sponsor will report any (S)ADEs and DD(s) to Health Canada and US FDA as required and within stipulated timelines.

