### **7.3.2 Causality or Relationship to the Device and/or Procedure**

- Unrelated: The AE has no temporal relationship to the device or to the procedure, and/or there is evidence of alternative cause such as concurrent medication or illness;
- Possibly related: A temporal relationship with the device or the procedure is not clear, alternative causes are also possible;
- Reasonable Causal Related: The AE is associated with the device or with procedures beyond reasonable doubt when:
  - The event is a known side effect of the product category the device belongs to or of similar devices and procedures;
  - The event has a temporal relationship with the device use/application or procedures;
  - The event involves a body-site or organ that the device or procedures have an effect on;
  - The AE follows a known response pattern to the medical device (if the response pattern is previously known);
  - The discontinuation of medical device application (or reduction of the level of activation/exposure) and reintroduction of its use (or increase of the level of activation/exposure), impact on the serious event (when clinically feasible);
  - Other possible causes (e.g., an underlying or concurrent illness/ clinical condition or/and an effect of another device, drug or treatment) have been adequately ruled out;
  - Harm to the participant is due to error in use;
  - The event depends on a false result given by the device used for diagnosis, when applicable;
  - In order to establish the relatedness, not all the criteria listed above might be met at the same time, depending on the type of device/procedures and the AE.

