### **9.4 Steps Taken to Control or Mitigate Risks**

In-depth recommendations, special precautions and instructions regarding patient selection, device handling, and device placement are included in the IFU for the SCOUT® System. It is also stated in the IFU

that the devices can only be used by physicians who have received appropriate training on how to use the device. Physician users are expected to be aware of the known and foreseeable safety risks associated with the use of the device including the surgical and/or non-surgical treatment of these conditions.

Risks associated with the use of the device under investigation are minimized through device design, investigator selection and training, pre-specified participant eligibility requirements, and risk-based monitoring to ensure adherence to the protocol. All AEs will be reported to the Sponsor as summarized in Section 7.3 and will be monitored internally for safety surveillance purposes.

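### Protocol 7.2 and 7.3 set different scopes for recording adverse events, and the 7.2 causality filter uses grades that the 7.3.2 scale does not contain

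*Protocol*

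**What the plan says.** **Collection, narrower wording.** Protocol 7.2 opens by stating that, "per the study AE CRF, the following adverse events of interest and device deficiencies will be collected". It then names six event types without any condition on causality. A final category admits "any AE that, in the opinion of the investigator, has a causal relationship (probable or definite) to the device or procedure", together with any device deficiency.

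**Collection, wider wording.** Protocol 7.3 says: "Any AE in this period, either serious, non-serious, whether deemed device-related or not, must be reported to the Sponsor immediately". It adds: "All AE (serious or non-serious) and DD will be documented in the eCRF". Protocol 9.4 follows the same scope: "All AEs will be reported to the Sponsor as summarized in Section 7.3".

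**Causality scale.** Protocol 7.3 requires a causality assessment ("The investigator will evaluate (S)AEs with regard to causality and seriousness"), and 7.3.1 directs the investigator to the criteria that follow it. These are the three grades in 7.3.2. The first is unrelated. The second reads "Possibly related: A temporal relationship with the device or the procedure is not clear, alternative causes are also possible". The third begins "Reasonable Causal Related: The AE is associated with the device or with procedures beyond reasonable doubt when".

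**SAP.** Under a safety-population heading, SAP 6.2.3 speaks of collecting and analysing events classed as related to the procedure or device. SAP 10 describes all reported AEs, with one table for all serious AEs (SAEs) and one for non-serious AEs above a frequency threshold, 5% being the example. Neither table has a causality condition. SAP 7.1 takes device safety (secondary endpoint 2) from a device-related field on the AE form.

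**The concern.** Safety is part of the registry's secondary objective, and the protocol gives two descriptions of what goes on the AE form. The narrower one is presented as what the form collects, so it may be what sites see when they enter data. Its causality filter uses two words that appear nowhere else in the protocol and have no definition, while the investigator is told to grade on a different scale.

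At stake is completeness. A classification rule can be settled at analysis, but an event that was never recorded may not be recoverable. The independent adjudicator in 7.4 is to review every serious event and every event that may be device-related, and can only review what was entered. With 3 to 7 centers, some sites might also follow 7.2 and others 7.3. The between-site comparison in SAP 6.5.2 would then partly reflect recording practice where safety is concerned.

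**Working it through.** No rate, threshold or power figure is attached to endpoint 2, so there is no plan figure to reproduce. The check is a comparison of texts, followed by arithmetic for scale.

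**Step 1: scope by type of event.** It is assumed here that possibly related ranks below probable; the protocol gives no mapping. *Unlisted* means not one of the six types in 7.2.

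| Event in the Device Period | In 7.2? | In 7.3 and 9.4? | Where it is needed |
|---|---|---|---|
| One of the six listed types, any grade | Yes | Yes | SAP 10; 7.4 if serious or possibly device-related |
| Device deficiency | Yes | Yes in 7.3 (9.4 mentions AEs only) | Protocol 7.3 |
| Unlisted AE, probable or definite | Yes | Yes | SAP 10, 7.4, endpoint 2 if device-related |
| Unlisted SAE, possibly related | No | Yes | SAP 10 SAE table, 7.4, endpoint 2 only if this grade counts |
| Unlisted SAE, unrelated | No | Yes | SAP 10 SAE table, 7.4 |
| Unlisted non-serious AE, possibly related | No | Yes | SAP 10 non-serious table if above threshold, 7.4, endpoint 2 only if this grade counts |
| Unlisted non-serious AE, unrelated | No | Yes | SAP 10 non-serious table if above threshold |

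The scopes differ in the last four rows. Everything in 7.2 is also in 7.3, so recording under 7.3 satisfies both.

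**Step 2: causality terms.** Protocol 7.2 uses probable and definite. Protocol 7.3.2 has unrelated, possibly related and reasonable causal related. No word is shared and no mapping is given.

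**Step 3: how much could be lost.** The six types in 7.2 are the same six that 9.3 lists as anticipated device effects: infection, reaction to materials, tissue or vascular trauma, inaccurate detection, inaccurate deployment and migration. They carry no filter, and all device deficiencies are collected. The loss is therefore confined to unlisted AEs graded below probable, for which the documents give no rate.

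**Step 4: scale, illustration only.** SAP 10 counts each participant once over the total population, taken here as 500.
- One omitted participant: 1/500 = 0.2 percentage points.
- Exact one-sided 95% upper bounds (the SAP states a one-sided interval but no direction; upper is assumed). For a count of zero the bound is 1 − 0.05^(1/500) = 0.597%. The others are Clopper-Pearson bounds.

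| Assumed count | Rate (bound) | With one omitted participant restored |
|---|---|---|
| 0 | 0.0% (0.597%) | 0.2% (0.945%) |
| 5 | 1.0% (2.091%) | 1.2% (2.355%) |
| 10 | 2.0% (3.369%) | 2.2% (3.615%) |

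- Non-serious table: 5% × 500 = 25, so an event type must affect more than 25 participants to appear at the example threshold.

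The starting counts and the single omission are assumptions. They show the scale of one event, not an estimate of the loss.

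**The case against.** **7.2 and 7.3 can both be followed.** A reader might infer that the two sections are mutually exclusive. They are not. Protocol 7.2 does not say that only its list may be recorded, it calls its list events of interest, and 9.4 points to 7.3 for reporting. A site that leaves out an AE breaches 7.3, and SAP 7.3 gives failure to report an SAE as an example of a major deviation. This stands, and it limits the point to a difference in scope that invites under-recording. It does not remove the point: 7.2 describes what the form collects, and a causality filter on other AEs has no purpose if every AE is entered.

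**Endpoint 2 may not move.** A reader might infer that the device-related rate is understated. The documents do not establish this. The closing item under the third grade in 7.3.2 speaks of establishing relatedness, and 7.2 glosses a causal relationship as probable or definite. Both suggest that only the top grade counts. This is inference and not a stated rule. If it is right, and that grade equals probable or definite, the rate is unchanged.

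**Unseen documents may settle the rest.** The AE form and the adjudicator's charter are not among the documents. They may define the response options and say whether adjudication overrides the investigator. The cut-off and the override are therefore missing detail, not shown errors. Likewise, the remark in Protocol 8 that a sample of AEs is independently reviewed need not conflict with 7.4, since the events that 7.4 names are a subset of all AEs.

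**Conclusion.** The point holds as an inconsistency in recording scope and in causality terms. Protocol 7.3 and 9.4 require every AE in the Device Period to be reported; 7.2 describes a smaller set, with a filter that the prescribed scale cannot express. If a site or the form follows 7.2, unlisted AEs graded possibly related or unrelated go unrecorded, and the SAP 10 tables and 7.4 adjudication are incomplete to that extent.

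The size is unknown and probably small, because the anticipated device effects and all deficiencies are collected under either section. On the investigator's classification, unlisted SAEs judged unrelated affect the SAE table but not endpoint 2. Endpoint 2 changes only if possibly related counts, assuming that the top 7.3.2 grade corresponds to probable or definite. The registry is descriptive, so no test result depends on this. It should be corrected because events not recorded may be lost and the correction is cheap.

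**What to change.** 1. Reconcile Protocol 7.2 with 7.3 and 9.4 so that all AEs and device deficiencies in the Device Period are recorded in the eCRF. Keep the 7.2 list as events of interest within that scope.
2. Replace probable and definite in 7.2 with the 7.3.2 grades, and check that the AE form fields follow.
3. Reword SAP 6.2.3 to agree with SAP 10.
4. If the sponsor prefers a narrower scope, change 7.3, 9.4, 7.4 and the SAP 10 tables together. The scope must not fall below what 7.2 already collects. Recording only SAEs, deficiencies and AEs graded possibly related or higher would fail that test: it would drop, for example, a non-serious infection graded unrelated, which 7.2 collects now, and it would leave the SAP 10 non-serious table incomplete.
5. As a secondary clarification, state in SAP 7.1 and SAP 10 which 7.3.2 grades count as device-related for endpoint 2, and whether the adjudicated classification is used. SAP v1.0 (30AUG2021) predates the adjudicator added in protocol V3.0 (21FEB2023), so it could not address this.

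Cost: wording in both documents, and form fields if they follow 7.2. No new role is needed. Sites that now work to 7.2 would complete more AE pages on the 24-hour timeline in 7.3, notably where neoadjuvant therapy falls within the Device Period and participation approaches 7 months.

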### 7.3 Reporting of safety related events

Adverse events and DD will be collected from the time the reflector is inserted into the participant (at biopsy) to the time the reflector is removed at surgery (Device Period) or until a study completion form is completed. Any AE in this period, either serious, non-serious, whether deemed device-related or not, must be reported to the Sponsor immediately after the investigator or coordinator has become aware of its occurrence. Reporting of an AE or DD to the Sponsor should take place within 24 hours upon becoming aware of the event, but not later than 3 calendar days. All AE (serious or non-serious) and DD will be documented in the eCRF. The AE/DD eCRF page should be submitted to the Sponsor within 24 hours even if all of the information is not available at the time of the initial contact. Sponsor contact for reporting: .

The investigator will evaluate (S)AEs with regard to causality and seriousness.

Reporting of serious incidents to the regulatory authorities will be reported per local regulations:

- Incident means any malfunction or deterioration in the characteristics and/or performance of the SCOUT® Surgical Guidance system, including use-error due to ergonomic features, any inadequacy in the information supplied by the manufacturer and any undesirable side-effect.
- Serious incident means any incident that directly or indirectly led, might have led or might lead to any of the following:
  - Death of a participant, user or other person,
  - Temporary or permanent serious deterioration of the participant's, user's or other person's state of health,
  - Serious public health threat;

Safety related events, which require preventive or corrective measurements intended to protect participants, may have to be reported to the local REBs/IRBs. The Sponsor will notify all other involved sites to report to their respective REBs/IRBs according to their requirements. The Sponsor will report any (S)ADEs and DD(s) to Health Canada and US FDA as required and within stipulated timelines.

#### 7.3.1 Severity Definition

- Mild: Generally transient & not interfering with daily activities;
- Moderate: Sufficiently discomforting to interfere with usual activities;
- Severe: AE that prevents normal daily activities.

The investigator will document their assessment of the relationship of the AE to the device using the criteria outlined below.

### **7.3.2 Causality or Relationship to the Device and/or Procedure**

- Unrelated: The AE has no temporal relationship to the device or to the procedure, and/or there is evidence of alternative cause such as concurrent medication or illness;
- Possibly related: A temporal relationship with the device or the procedure is not clear, alternative causes are also possible;
- Reasonable Causal Related: The AE is associated with the device or with procedures beyond reasonable doubt when:
  - The event is a known side effect of the product category the device belongs to or of similar devices and procedures;
  - The event has a temporal relationship with the device use/application or procedures;
  - The event involves a body-site or organ that the device or procedures have an effect on;
  - The AE follows a known response pattern to the medical device (if the response pattern is previously known);
  - The discontinuation of medical device application (or reduction of the level of activation/exposure) and reintroduction of its use (or increase of the level of activation/exposure), impact on the serious event (when clinically feasible);
  - Other possible causes (e.g., an underlying or concurrent illness/ clinical condition or/and an effect of another device, drug or treatment) have been adequately ruled out;
  - Harm to the participant is due to error in use;
  - The event depends on a false result given by the device used for diagnosis, when applicable;
  - In order to establish the relatedness, not all the criteria listed above might be met at the same time, depending on the type of device/procedures and the AE.

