3.2 Endpoints

Primary Endpoint: The number of patient visits to the breast center for invasive procedures from the time of biopsy to surgery.

Secondary Endpoint:

1. Device success: percent successful localization, detection and retrieval;
2. Device safety: rate of device-related adverse events;
3. Procedural success: absence of close margins (DCIS: <2mm), positive margins (tumor on ink) or requirement for re-excision.
4. Duration (days) from assessment to surgery and biopsy to surgery;
5. Radiologist assessment: ease of placement; ability to position reflector in desired location; scheduling flexibility; visibility on ultrasound/ mammography (immediate and late); artifact (Tomo/MRI if applicable).
6. Surgeon assessment: ease of detection; ease of device retrieval.
7. Participant satisfaction questionnaire: anxiety; convenience; pain; overall experience compared to expectation
8. Process improvement with implementation of same-day biopsy and SAVI SCOUT® placement.

[figure not shown]
4 Study Methods

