7.1 Variable Assessment

Variable	CRF and data point
Inclusion	Inclusion CRF_Reflector Location
Per protocol completion	Surgery CRF_Type of surgery
Intention to treat completion	Study Completion CRF_Reason for completion
Device insertion success	Inclusion CRF_Deployment within lesion
Device retrieval success	Surgery CRF_Reflector retrieval success
Procedural success	Outcomes CRF_Margin assessment
Efficiency endpoint	Additional visit CRF_Number of visits
Device Safety	Adverse Event CRF_Device Related

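### Protocol 7.3.2 grades device and procedure causality together and has no middle grade for a well-timed event with a competing cause, so the device-related rate can err in either direction

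*Protocol*

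**What the plan says.** The safety endpoint, in both Protocol 4.2 and SAP 3.2, is "Device safety: rate of device-related adverse events". It names the device and not the procedure.

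Protocol 7.3.1 sets the task: "The investigator will document their assessment of the relationship of the AE to the device using the criteria outlined below". The criteria that follow in 7.3.2 form one scale with three grades:

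- The lowest, *Unrelated*, covers an event that has no link in time to device or procedure, "and/or there is evidence of alternative cause such as concurrent medication or illness".
- The middle one is named *Possibly related*, and its whole definition reads "A temporal relationship with the device or the procedure is not clear, alternative causes are also possible".
- The highest, named *Reasonable Causal Related*, begins "The AE is associated with the device or with procedures beyond reasonable doubt when" and then lists conditions. A closing note says that they need not all be met together.

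Other sections do single out the device. Protocol 7.1 defines an adverse device effect as "An adverse event related to the use of the device", and extends this to deployment and implantation. SAP 7.1 takes device safety from a case report form item, "Adverse Event CRF_Device Related", and SAP 10 plans a separate rate for adverse device effects. SAP 6.2.3, by contrast, describes the safety analysis in terms of events that are procedure-related or device-related. Protocol 7.4 gives an independent physician, at minimum, the serious and the potentially device-related events.

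**The concern.** There are two separate problems.

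First, the question asked (relationship to the device) and the criteria supplied (device or procedure) do not match. The reflector goes in at a diagnostic biopsy and comes out at breast surgery. Infection and tissue or vascular trauma, both listed in Protocol 7.2 as events of interest, can follow a biopsy or an operation with no reflector present. If such an event is graded related because of the procedure, it can be counted in a rate that will be read as the device's own.

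Second, the grades are neither exclusive nor exhaustive. An event with clear timing and a competing explanation can be pushed down to *Unrelated*, with no middle grade to stop it.

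At stake is the meaning of the registry's only safety endpoint. The planned neoadjuvant comparison in SAP 6.3, which includes safety, is also exposed: concurrent medication is a named route to *Unrelated*, so downgrading could be more common in that subgroup than in the full cohort.

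**Working it through.** The plan gives no expected device-related rate, so there is no figure to reproduce. The check is a reading of the rules against each other.

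**Step 1: what is being graded.**

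| Place | Target |
|---|---|
| Endpoint (Protocol 4.2, SAP 3.2) | Device |
| Instruction (Protocol 7.3.1) | Device |
| Adverse device effect (Protocol 7.1) | Device use, including deployment |
| All three grades (Protocol 7.3.2) | Device or procedure |
| Residual reportable category (Protocol 7.2) | Device or procedure |
| Safety population (SAP 6.2.3) | Procedure or device |
| Source field (SAP 7.1) | Device |

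The field that feeds the endpoint is labelled for the device, but the only criteria in either document for completing it are the joint ones. The word procedure is not tied to biopsy, insertion or surgery.

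**Step 2: which events are exposed.** Protocol 4.6 collects no events before insertion. Protocol 7.3 collects from insertion to removal at surgery, or to the study completion form; SAP 6.2.3 runs to completion of surgery. The exposed events are those arising in the biopsy session after insertion, in the interval before surgery, and during the operation. Later surgical complications are outside the window.

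**Step 3: whether the grades cover the cases.**

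| Timing | Other cause | Grades whose wording is met |
|---|---|---|
| None | Any | *Unrelated* |
| Unclear | Possible | *Possibly related* |
| Unclear | Evidence for it | *Unrelated* and, arguably, *Possibly related* |
| Clear | None | Top grade |
| Clear | Possible, no evidence | Neither lower grade; top grade only if its certainty standard is met |
| Clear | Evidence for it | *Unrelated*; top grade arguable under the closing note; no middle grade |

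The last two rows show the gap. The third and sixth show that one event can satisfy two grades.

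**Step 4: from grade to rate.** Neither document says whether *Possibly related* counts as device-related. Protocol 7.2 uses *probable* and *definite*, which are not grades of this scale.

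**Step 5: scale.** SAP 10 counts each participant once over the total population. With 500 enrolled, one participant moved in or out changes the rate by 1/500 = 0.2 percentage points. How many would move cannot be derived: the documents give no biopsy or surgical complication rate, no neoadjuvant share and no view of the adverse event form.

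**The case against.** The best defence is that the plan intends a device-only judgement. Protocol 7.1 defines the adverse device effect by device use, the SAP has its own device field and its own rate, and one scale can be applied once to the device and once to the procedure. The adverse event form is not among the documents and may do this. That stands as a limit on the conclusion: a reader might infer that procedural complications are being counted against the device, but the documents show only that they can be. The defence does not remove the problem, because no device-only criteria are written down.

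A reader might also infer that any alternative cause makes an event *Unrelated*. The text requires evidence of one, and being on neoadjuvant therapy is not by itself evidence that it caused a reflector-site infection. The closing note also leaves the top grade open to such an event, although that sits awkwardly with a standard of certainty.

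On adjudication, it is fair to say that *potentially device-related* is not tied to the investigator's grade and that the charter may widen the remit. So a non-serious event graded *Unrelated* may miss review; it cannot be said that it will. Protocol 8 speaks of review of only a sample of events, which gives little reassurance. A downgraded event would leave the rate but should remain visible, since Protocol 7.3 requires all adverse events in the eCRF.

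Finally, a reader might try to express the distortion as a multiple of the complaint rates in Protocol 9.3. The documents do not support this. The base could be 0.48% (the largest category maximum) or 0.02 + 0.08 + 0.48 + 0.22 + 0.02 = 0.82% (all five maxima). These are annual complaint rates, not per-participant event rates, and the procedural rate would be pure assumption.

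**Conclusion.** The defect is real and should be corrected. As written, the scale can admit biopsy or surgical events within the collection window to the device-related rate, and can let well-timed events with evidence of another cause leave it. The two errors run in opposite directions, so neither the net sign nor the size can be stated.

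The conclusion rests on Protocol 7.3.2 being the operative criteria for the form's device field; if the form or the adjudication charter already holds device-only criteria, the first half falls away and only the wording needs aligning. The overlap and gap between grades do not depend on that. The endpoint is descriptive, and Protocol 5.3 sets no pass/fail criterion, so what suffers is the interpretation of the reported rate, not a formal decision.

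**What to change.** In Protocol 7.3.2 and the adverse event form:

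1. Grade relationship separately to (a) the reflector and SCOUT system, including deployment, and (b) the procedures, naming biopsy and surgery.
2. Calculate the safety endpoint from (a) only and tabulate (b) beside it.
3. Require for *Unrelated* either no plausible temporal relationship or an alternative cause that fully explains the event.
4. Let *Possibly related* include clear timing with a competing cause.
5. State which grades count as device-related.
6. Align the causality terms in Protocol 7.2, and SAP 6.2.3 and 7.1, with the revised scale.

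The cost is protocol and SAP wording, one or two added fields on the form, and re-grading of events already entered. Where biopsy and insertion share a session and a site, attribution between them will sometimes stay uncertain. Separate fields make that uncertainty visible but do not remove it.
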